In case of discontinuation, subjects will undergo a remote Early Trial Discontinuation Visit aimed to assess physical abnormalities, vital signs and transdermal oxygen saturation measurement.

Replacement Procedures

No patient who has been randomized and withdraws from the study for any reason will be replaced.

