9.5.4. Analysis of safety variables

TEAEs, ADRs and TESAE will be presented by treatment arms in terms of number of AEs and incidence by System Organ Class (SOC) and Preferred Terms (PT) using MedDRA. Analyses will be provided also by severity and relationship to the study drug. In addition, time-to-event methods will be used to summarize the overall survival.

Vital signs and laboratory tests will be presented using descriptive statistics at each available visit. Additionally, the frequency of subjects reporting an abnormal or abnormal clinically significant laboratory value will be presented for each laboratory parameter. Shift tables versus baseline will compare abnormal laboratory findings at each post-baseline visit.

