7.3 EARLY WITHDRAWAL FROM THERAPY OR ASSESSMENT AND END OF STUDY

7.3.1 EARLY TRIAL DISCONTINUATION VISIT AND UNSCHEDULED VISITS

In general, for by-visit summaries, data recorded at the nominal visit will be presented.

Unscheduled measurements will not be included in by-visit summaries. Listings will include scheduled, unscheduled, and early trial discontinuation visit (ETDV).

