15.2 VITAL SIGNS

The following vital signs (blood pressure [BP], pulse rate [PR], body temperature [BT]), transdermal oxygen saturation (SpO₂) will be collected for patients.

Vital signs measurements will be summarized by treatment using descriptive statistics for each available visit, including change from baseline.

All vital signs findings will be listed, including data from the unscheduled visits.

15.3 LABORATORY PARAMETERS: BLOOD (HEMATOLOGY & BIOCHEMISTRY), COAGULATION, VIROLOGY AND OTHER MARKER

The following biomarker parameters at Day 7, 14, 21 and 28 after randomization will be summarized using descriptive statistics by visit and treatment:

- Complete blood cell counts
- Hepatic function (ALT, AST and bilirubin)
- Coagulation (PT, aPTT and INR)
- Other marker including (D-dimer, CPK, LDH)

Depending on the nature of the variable (continuous or categorical) the change from baseline values or shift tables comparing baseline and each post-baseline qualitative results of laboratory findings will be presented.

Mean (+/-) Standard Error Plot will be plotted for the change from baseline results of the above-mentioned laboratory parameters by visit and treatment. Analyses will be performed on SAF population.

Actual results and change from baseline for quantitative laboratory parameters will be summarised descriptively by treatment and visits. In addition, shift tables for laboratory parameters comparing values (Low, Normal and High) using the standard reference ranges will be presented for the baseline laboratory measurements vs. each post-baseline visit measurements.

Additionally, the frequency of patients reporting an abnormal or abnormal clinically significant laboratory value will be presented for each laboratory parameter.

For any Patient, if more than 1 results per visit and per lab parameters are available then the latest one will be considered based the date and time.

All laboratory results will be listed.

The below list of lab parameters results will be collected for patients.

Table 4: List of Lab parameters

Biochemistry (T0, T7, T14, T21, T28)	Haematology (T0, T7, T14, T21, T28)	Coagulation (T0, T7, T14, T21, T28)

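### Laboratory tables use the latest same-visit result and omit unscheduled draws, with no worst-value summary, so transient abnormalities may be understated

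*SAP*

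**What the plan says.** SAP 15.3 (laboratory parameters) plans descriptive summaries of values and changes from baseline, standard-error plots, shift tables against the reference range for each post-baseline visit, and a frequency table: "the frequency of patients reporting an abnormal or abnormal clinically significant laboratory value will be presented for each laboratory parameter". Protocol 9.5.4 promises the same table: "the frequency of subjects reporting an abnormal or abnormal clinically significant laboratory value will be presented for each laboratory parameter". Neither document says whether that table is by visit or at any time, or whether superseded or unscheduled results count.

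The next sentence of SAP 15.3 sets the selection rule: "if more than 1 results per visit and per lab parameters are available then the latest one will be considered", judged by date and time. It makes no exception for the frequency table.

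SAP 7.3.1 sets the general rule for visit tables: "In general, for by-visit summaries, data recorded at the nominal visit will be presented", and "Unscheduled measurements will not be included in by-visit summaries". It mentions the early trial discontinuation visit only in connection with listings.

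Two provisions work the other way. SAP 15.3 states that "All laboratory results will be listed". Protocol 6.2.4 has the investigator review laboratory results and record clinically relevant changes as adverse events. Neither document plans a worst post-baseline or worst-grade laboratory table.

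**The concern.** A laboratory test is more likely to be repeated when the first result is abnormal or unexpected. Keeping the latest result then tends to keep values that have returned to normal. Leaving out unscheduled draws also removes from the by-visit tables any abnormality first seen between nominal visits. A safety table should show whether a patient was ever abnormal on treatment, and no planned table is defined so that it certainly does this.

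The choice also sits oddly with the rest of the SAP. Section 15.1.2 classifies repeated adverse events by the most severe level, section 15.1.1 treats events with a missing start date as treatment-emergent, and section 12 classifies doubtful medications by the worst case. Protocol 9.5.4 attaches no latest-value restriction to its abnormal-value frequency, and SAP section 18 does not list the restriction as a change.

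At stake is the between-arm comparison of platelets, liver enzymes, coagulation and the other panels. Protocol 2.5.3 says that the safety profile of raloxifene in COVID-19 is not known, and SAP 4.3 reports that enrolment stopped at 68 patients. At that size, one or two patients per arm can change how a table reads.

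**Working it through.** The documents state no figure for this point, so there is none to reproduce. The check traces what each rule does to a result and then illustrates the size under assumptions.

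**What happens to an abnormal result**

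| Situation | By-visit tables | Abnormal-value frequency | Listings |
|---|---|---|---|
| Abnormal scheduled result, normal re-test filed under the same visit | abnormal value replaced | replaced, as written | both shown |
| Abnormal scheduled result, normal re-test filed as unscheduled | abnormal value kept | kept | both shown |
| Abnormality seen only at an unscheduled draw | absent | not specified | shown |
| Normal scheduled result, abnormal later result under the same visit | abnormal value shown | shown | both shown |

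The two rules are therefore alternatives for a given re-test and do not compound. The latest-value rule loses an abnormal value only in the first row.

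**Size of the first-row loss**

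Inputs, none of them in the documents and all assumed:
- p: share of patients with an abnormal scheduled value at a visit
- r: share of those re-tested under the same visit
- q: share of the re-tests that are normal

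Displayed rate = p × (1 − r × q).

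For p = 20%:
- r = 0: 20% × 1 = 20%
- r = 10%, q = 50%: 20% × 0.95 = 19.0%
- r = 25%, q = 50%: 20% × 0.875 = 17.5%
- r = 50%, q = 75%: 20% × 0.625 = 12.5%

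Patients hidden per arm per visit = n × p × r × q. With the 68 patients of SAP 4.3 split equally (an assumption), n = 68/3 ≈ 22.7. At r = 50% and q = 75% this gives:
- p = 10%: 22.7 × 0.10 × 0.375 ≈ 0.85
- p = 20%: 22.7 × 0.20 × 0.375 ≈ 1.7
- p = 30%: 22.7 × 0.30 × 0.375 ≈ 2.55

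At r = 0 it is zero in each case.

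**Any-time count**

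There are four post-baseline visits (T7, T14, T21, T28). If visits are treated as independent, which is a simplification, the share ever abnormal is 1 − (1 − rate)⁴. For p = 20%, the share with every scheduled abnormality counted is 1 − 0.8⁴ = 59.0%. Under the latest-value rule it is 1 − 0.825⁴ = 53.7% (r = 25%, q = 50%) or 1 − 0.875⁴ = 41.4% (r = 50%, q = 75%). The relative loss per patient is smaller than per visit, because a patient abnormal at two visits drops out only if both values are replaced.

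**Between arms**

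If r and q are equal across arms, the risk ratio is unchanged and the risk difference shrinks by (1 − r × q). For assumed rates of 30% and 10%, r = 25% and q = 50% give 26.25% and 8.75%: the ratio stays at 3 and the difference falls from 20 to 17.5 points.

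**The case against.** The strongest reply is that nothing is lost. Every laboratory result is listed, and clinically relevant changes become adverse events and enter the TEAE tables at their most severe level. Thrombocytopenia, the most obvious platelet concern, is an event of special interest with its own summary (SAP 15.1.2). None of this depends on the latest-value rule. The reply stands for clinically relevant abnormalities. It does not cover abnormal values that the investigator judges not relevant. Both documents promise a count of abnormal values as well as of clinically significant ones, and a listing gives no comparison between arms.

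A second reply is that same-visit repeats may be rare. Blood is drawn at home by a nurse on days 0, 7, 14, 21 and 28 (Protocol 6.2.2), and no repeat draw is scheduled. That is a fair inference, and it is why r is left open down to zero.

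A third is that the latest value may be the worse one, or may correct a faulty sample. This also stands. The direction is a tendency and not a certainty, and replacing latest with first would be largely a matter of preference.

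A reader might also infer that discontinuation-visit laboratory values are dropped. The documents do not support this: that visit is a "remote Early Trial Discontinuation Visit aimed to assess physical abnormalities, vital signs and transdermal oxygen saturation measurement", with no blood sample named. It bears on vital signs and SpO2 only, and its absence from by-visit summaries is implied, not stated. The latest-value rule itself covers laboratory parameters, not vital signs.

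**Conclusion.** The concern holds as a gap in the tabulated safety summaries. The latest-value rule and the exclusion of unscheduled draws are both stated, and no worst-value table offsets them. Transient laboratory abnormalities may be understated in the tables, mainly those not judged clinically relevant.

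The size cannot be determined, because r and q are not documented. Under the assumed ranges, a 20% abnormal rate at a visit is displayed as anything from 20% down to 12.5%, which hides 0 to about 1.7 patients per arm. Over p = 10% to 30%, the range is 0 to about 2.6 patients per arm.

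Two stronger readings are tempting. One is that abnormal values are erased and laboratory harm is understated as a matter of fact. The listings and the adverse-event route contradict the first half, and the unknown r, q and direction leave the second unproven. The other is that the planned tables cannot show the abnormal-value frequency that the protocol promises. The scope of that table is unspecified, so it could still be programmed to count any post-baseline result. The defect is that the SAP does not say so, and that the sentence which follows points the other way.

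**What to change.** Keep the by-visit descriptive tables. In SAP 15.3:

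1. State that the frequency of abnormal and of abnormal clinically significant values counts a patient with any such post-baseline result, whether scheduled, repeat or unscheduled, and that the latest-value rule does not apply to this table.
2. Add one shift table per laboratory panel from baseline to the worst post-baseline value, on the same data. State for each parameter whether worst means lowest, highest or both.
3. State how re-tests are assigned to visits, so that the by-visit tables can be read.

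Separately, in SAP 15.2, add a worst post-baseline row for vital signs and SpO2 that includes unscheduled and discontinuation-visit values.

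The data are already collected and listed, so the cost is SAP wording and limited programming. Abnormal counts will look slightly less favourable, and an occasional spurious result will be counted. The listings allow such results to be identified.

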16 PREGNANCY TEST OVER THE STUDY

Data will be summarized for the SAF population. Pregnancy tests will be performed at T0, T7 and T14 visits.

A summary table showing test results (Negative/Positive) over the study will be produced by treatment group.

17 GENERAL PROGRAMMING SPECIFICATIONS

Tables, Figures and Listings will be generated as per the shells template.

All statistical analysis and output will be generated using SAS, all the reports will be printed in RTF format. All output will be in landscape orientation.

Table Format Specification:

- a. In summary tables of quantitative variables, the minimum and maximum statistics will be presented to the same number of decimal places as the raw (observed) data. The estimated mean and median for a set of values will be reported to one more decimal place than the raw (observed) data and rounded appropriately. The standard errors (or standard deviations [SD]) and the confidence intervals will be reported to two additional decimal places than the raw (observed) data and rounded appropriately.
- b. Data in columns of a table will be formatted as follows:
 - i. Alphanumeric values will be left-justified (in mixed and upper- and lower-case)
 - ii. Whole numbers (e.g. counts) will be right justified
 - iii. Numbers containing fractional portions will be decimal aligned
- c. All fractional numeric values will be reported with a zero to the left of the decimal point (e.g. 0.12-0.3).
- d. In summary tables of qualitative variables, counts and percentages will be used. The denominator for each percentage will be the number of patients within the population under respective treatment group unless otherwise specified. Percentages will be reported to one decimal places
- e. When no data are available for a table or Listings or figures, an empty page with the title will be produced with suitable text. Example: THERE WERE NO SERIOUS ADVERSE EVENTS.
- f. The default tables, figures and listings (TFL) layout will be as follows

Orientation	Landscape
Paper Size	A4
Margins	Top: 2.5 cm Bottom: 2.5 cm Left: 2 cm Right: 2 cm
Font	Courier new8-point

Headers	1. The header will appear on the top left corner of each page of the output, containing the protocol number (RLX0120) and sponsor name (Dompé). The page number, in the format of “Page x of y”, will appear on the top right corner of the output, where y = last page of corresponding output. Table status (draft or final). 2. Any TFLs generated prior to database lock or completion of TFL validation will be marked “Draft”.
Footers For Tables	The SAS program name, Reference Listings and the date and time of the creation of the output (run date and time) will appear on the bottom left corner as follows: 1. Reference Listings: listing Number 2. Source:[program name].sas, Run on : DDMMYY:hh:mm:ss
Footers For Listings and Graphs/Figures	The SAS program name, and the date of the creation of the output (run date) and CRF Source will appear on the bottom left corner as follows: 1.CRF Source: 2.Source: [program name]. sas, Run on DDMMYY:YY

18 CHANGES FROM PROTOCOL

Following are the changes from the protocol:

- a. Specification of additional populations-All Patient Enrolled (ENR) and Randomized Population (RND).
- b. Text “Subjects”, “Participants” changed to “Patients”.
- c. Baseline characteristics “gender” and “Child-bearing potential status” are combined and derived a new categorical variable with categories Male, Female pre-menopausal status and Female post-menopausal status to be included as factor “Status” in the statistical model of analysis of efficacy endpoints.
- d. Due to the premature interruption of the enrolment, no interim analysis will be done.

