9.5.2. Analysis of efficacy variables

9.5.2.1. Primary analyses

The proportion of subjects with undetectable SARS-CoV-2 at PCR at day 7 after randomization (virologic endpoint) and the proportion of subjects who not requires supplemental oxygen therapy (NEWS ≤ 2) and/or mechanical ventilation at day 14 after randomization (clinical endpoint) will be separately analyzed by means of logistic regression models adjusting by pre-defined factors as center, age, gender and post-menopausal status. Additional covariates may be defined in the SAP. Each treatment arm will be compared independently with the placebo.

The null hypothesis for the virologic endpoint is that proportion of treated subjects with undetectable SARS-CoV-2 at PCR at day 7 after randomization is lower or equal the placebo one ($\pi_{PLACEBO}$). Two sets of null and alternative hypotheses are provided, one for each treatment dosage:

$$H_{01-60mg}: \pi_{RALOXIFENE-60mg} \leq \pi_{PLACEBO}$$

$$H_{01-120mg}: \pi_{RALOXIFENE-120mg} \leq \pi_{PLACEBO}$$

$$H_{11-60mg}: \pi_{RALOXIFENE-60mg} > \pi_{PLACEBO}$$

$$H_{11-120mg}: \pi_{RALOXIFENE-120mg} > \pi_{PLACEBO}$$

The null hypothesis for the clinical endpoint is that proportion of treated subjects who not requires supplemental oxygen therapy (NEWS ≤ 2) and/or mechanical ventilation at day 14 after randomization is lower or equal the placebo one ($\pi_{PLACEBO}$). Two sets of null and alternative hypotheses are provided, one for each treatment dosage:

$H_{02-60mg}: T_{RALOXIFENE-60mg} \leq \pi_{PLACEBO}$ $H_{02-120mg}: T_{RALOXIFENE-120mg} \leq \pi_{PLACEBO}$ $H_{12-60mg}: T_{RALOXIFENE-60mg} > \pi_{PLACEBO}$ $H_{12-120mg}: T_{RALOXIFENE-120mg} > \pi_{PLACEBO}$

Superiority of raloxifene will be claimed if at least one null hypothesis is rejected, at interim or at final analysis according to criteria shown in section 9.3.

Sensitivity analyses will be defined in the SAP to assess the robustness of results on primary endpoints versus the presence of missing data (unexpected) and the presence of protocol deviations.

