9.5.6. Specification of subgroups for analysis

Statistical tests for interaction (between subgroup and treatment arm) will be performed to decide about the need to further investigate subgroups of the trial population based on the following variables: age group, gender and Country.

Subgroup analysis will be performed if interaction tests are statistically significant at 15% nominal level. Statistical details and potential new subgroups definitions will be reported in the SAP.

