8 STATISTICAL METHODOLOGY AND CONSIDERATIONS

8.1 ADJUSTMENTS FOR COVARIATES AND FACTORS TO BE INCLUDED IN ANALYSES

In the analysis of primary endpoints and secondary endpoints, the following factors/covariates will be considered in the Binary Logistic regression and Repeated Measures Logistic regression model as described in the SAP section 14.1

- Treatment group;
- Center;
- Age group;
- Status (Male, Female pre-menopausal status, Female post-menopausal status);
- For Clinical outcome: Baseline NEWS value.

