8.5 EXAMINATION OF SUBGROUPS

Statistical tests for interaction (between subgroup and treatment arm) will be performed to decide about the need to further investigate subgroups of the trial population based on the following variables:

- age group (< median vs \geq median, where median is calculated based on ENR population)
- gender (Male vs Female)
- Status (Male, Female pre-menopausal status, Female post-menopausal status);

Subgroup analysis will be performed if interaction effects are statistically significant at 0.15 level of significance.

Subgroup analysis will be performed for the primary efficacy endpoints. Descriptive and appropriate inferential statistical tests will be used. All subgroups will be analysed using FAS population.

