14 ANALYSES OF EFFICACY VARIABLES

14.1 EFFICACY ANALYSES

NEWS score evaluation will be performed at T0, T7, T14 and T28. NEWS score and NEWS score parameters as per collected in CRF will be provided in Listing for FAS population. Refer Appendix 3 for NEWS score.

Table 3: Summary of Analyses Strategies for efficacy endpoints:

Endpoint	Analysis set	Statistical method	Factors/Co variates	Missing data Handling	Analyses type
Virologic outcome - Proportion of patients with undetectable SARS-CoV-2 at PCR at day 7 after randomization.	FAS	Binary Logistic regression	Treatment, center, age and status	Missing data will not be imputed	Primary analysis
Virologic outcome - Proportion of patients with undetectable SARS-CoV-2 at PCR at day 7 after randomization.	PP	Binary Logistic regression	Treatment, center, age and status	Missing data will not be imputed	Sensitivity analysis
Clinical outcome - Proportion of patients who does not require supplemental oxygen therapy (NEWS ≤2) and/or mechanical ventilation at day 14 after randomization.	FAS	Binary Logistic regression	Treatment, center, age, status and baseline NEWS	Missing data will not be imputed	Primary analysis
Clinical outcome - Proportion of patients who does not require supplemental oxygen therapy (NEWS ≤2) and/or mechanical ventilation at day 14 after randomization.	PP	Binary Logistic regression	Treatment, center, age, status and baseline NEWS	Missing data will not be imputed	Sensitivity analysis

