14.1.1 PRIMARY EFFICACY ENDPOINTS AND ANALYSES

1. Proportion of patients with undetectable SARS-CoV-2 at PCR at day 7 after randomization (virologic endpoint). This endpoint will be derived as below.
 - Based on Approved molecular test (PCR) result at day 7, the responses will be considered as “detectable” if PCR result is “Positive” otherwise “undetectable” if PCR result is “Negative” (Missing PCR result will be considered as missing in the main analysis).

The response (detectable / undetectable) at day 7 will be analysed using Binary logistic regression model with treatment group and pre-defined baseline factors (center, age, status and their interaction effects with treatment group). Odds ratio

will be computed for comparisons of each active treatment group versus placebo. i.e., raloxifene (60 mg) versus placebo and raloxifene (120 mg) versus placebo.

2. The proportion of patients who does not require supplemental oxygen therapy (NEWS ≤ 2) and mechanical ventilation at day 14 after randomization (clinical endpoint). This endpoint will be derived as below.

- If collected NEWS score > 2 or mechanical ventilation at day 14 result “Yes” then the response will be considered as “Required”. If collected NEWS score ≤ 2 and mechanical ventilation with result “No” then the response will be considered as “Not Required” (if both NEWS score and mechanical ventilation are missing, patient will be considered as missing).

The response (Required/ Not required) at day 14 will be analysed using Binary logistic regression model with treatment group and pre-defined baseline factors (center, age, status, baseline NEWS and their interaction effects with treatment group). Odds ratio will be computed for comparisons of each active treatment group versus placebo. i.e., raloxifene (60 mg) versus placebo; and raloxifene (120 mg) versus placebo.

For both virologic and clinical endpoint, Binary Logistic regression will be performed using PROC GENMOD in SAS® on the observed data only to estimate difference in proportions between each active treatment versus placebo and its corresponding 95% (2-sided) confidence intervals. Exponential transformation will be used to obtain the odds ratio and corresponding 95% confidence interval. P-values will be reported based on the Wald tests from Type III analyses. Bonferroni method will be considered to handle multiple treatment comparisons.

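### The SAP gives two codings of age for the same primary models: age group in section 8.1, age in Table 3, 14.1.1 and 14.1.2

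*SAP*

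**What the plan says.** Protocol 9.5.2.1 analyses both primary endpoints by logistic regression, "adjusting by pre-defined factors as center, age, gender and post-menopausal status", and adds that "Additional covariates may be defined in the SAP". It does not say whether age is continuous or grouped. The protocol uses the term age group only in 9.5.6, where the subgroup variables are "age group, gender and Country".

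The SAP names the age covariate in four places:

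- **Section 8.1** lists age group among the factors for the binary logistic model and the "Repeated Measures Logistic regression model as described in the SAP section 14.1". It gives no levels and does not cite 8.5.
- **Table 3 (14.1)** gives the virologic model as "Treatment, center, age and status". The clinical model adds baseline NEWS.
- **Section 14.1.1** gives the virologic model as "center, age, status and their interaction effects with treatment group". The clinical model has the same form with baseline NEWS added.
- **Section 14.1.2** lists age for the repeated-measures secondary models.

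The only definition of age group is in 8.5, for subgroup tests: below the median versus at or above it, "where median is calculated based on ENR population". By 5.1 the ENR population is everyone who gave consent. By 5.3 the models are fitted on the FAS, which is randomized and dosed patients.

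Section 18 lists four changes from the protocol. The only covariate change is the new Status factor ("Female pre-menopausal status and Female post-menopausal status to be included as factor"). Age does not appear.

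**The concern.** The protocol keeps age (model) and age group (subgroups) apart, so the two terms cannot be taken as synonyms. A programmer following 8.1 and one following 14.1.1 would fit different primary models, and both could call their result pre-specified. Section 18 shows that recoding a named covariate was thought worth declaring, since it does so for sex and menopausal status. If 8.1 governs, a change to the primary model is undeclared. If 14.1 governs, 8.1 is wrong. Either way a line needs correcting.

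Three things are at stake: which result is reported when the two models fall on opposite sides of the threshold; whether the model can be fitted at all at the sample size reached; and whether the choice is closed before the codes are opened.

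**Working it through.** **Plan's own figure.** The documents give no figure on age, so there is none to reproduce. For the threshold, 2 endpoints × 2 doses gives one-sided 0.025/4 = 0.00625, z = 2.498. The divisor of 4 is consistent with protocol Table 1: a two-look Pocock constant at one-sided 0.00625 and information fraction 0.5 comes out at 2.6964, against the printed 2.69640. With no interim analysis (SAP 4.3), 2.498 is the single-look threshold.

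**Inputs from the documents.** 68 patients enrolled (SAP 4.3), and 68/3 ≈ 23 per arm; age at least 40 (protocol 4.1); design rates 25% v 50% and 50% v 75% (protocol 9.1).

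**Assumptions, not in the documents.** Age roughly normal, truncated at 40; odds ratio for age between 1 and 3 per SD; no other covariates in the model.

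**Age variation lost by a median split.** The share kept is the squared correlation of age with its above-median indicator. For a normal variable this is 2/π = 0.637, so 1 − 0.637 = 36% is lost. For normals truncated at 40 the loss is 34–37%, for a uniform on 40–80 it is 25%, and for an exponential starting at 40 it is 52%.

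**Main-effects models, simulated, 23 per arm, z > 2.498.**

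- At 50% v 75%, power with age in years v age group was 22.1% v 21.2% (age odds ratio 2), a gain of 0.9 points, and 24.4% v 21.8% (odds ratio 3), a gain of 2.6 points.
- A separate simulation at N = 68, 25% v 50%, with age odds ratios of 1.0, 0.67 and 0.5 per SD, gave power within 1 point between codings. The standard error of the treatment log-odds ratio was 0.684 v 0.684, 0.689 v 0.686 and 0.710 v 0.698 (years v group).
- The two codings disagreed on significance in about 2–7% of trials.

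**Chance imbalance in age.** With age group, a 1-SD difference in mean age between arms shifts the treatment z by about −0.26 (odds ratio 2) or −0.47 (odds ratio 3). With 23 per arm the standard error of that difference is √(2/23) = 0.295 SD. A typical imbalance therefore shifts z by 0.295 × 0.26 = 0.08 or 0.295 × 0.47 = 0.14.

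**With the age-by-treatment interaction of 14.1.1.**

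| Age coding | Trials with no finite fit |
|---|---|
| Median split | 9–47% |
| Continuous | about 0.3–6% |

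The ranges run over the assumed response rates and age effects. The mechanism is simple: the split gives six arm-by-age cells of 11 or 12 patients, and a cell with all or no responders sends an estimate to infinity. For non-convergence, 14.1.1 prescribes exact fitting, then removal of covariates one at a time by significance, then an unadjusted Fisher test.

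**Centring.** If age enters uncentred with its interaction, the treatment term is the effect at age 0. The power of that term at z > 2.498 was below 1%. In one setting (mean age 58, SD 10, odds ratio 2 per SD, treatment log-odds ratio 1.25) it was 0.3% uncentred, 20% centred, and 15% for a two-level age averaged over its levels.

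**The case against.** **Section 8.1 defers to 14.1.** The strongest reply is that 8.1 describes its list as belonging to the models set out in 14.1, and 14.1 keeps age. On that reading nothing has changed from the protocol and section 18 has nothing to declare. This stands as far as it goes: a reader might infer that the SAP replaced age without declaring it, and the documents do not show that. They show an unresolved conflict, since no sentence gives either section precedence.

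**Two levels are inferred.** A reader might also infer that the model contains a two-level age. That is the likely reading of 8.1, because 8.5 holds the only definition, but 8.1 does not say so.

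**The information loss is easily overread.** It is tempting to say that a third of the information is lost. The 36% needs a normal age distribution, the range over other shapes is 25–52%, and it is variation in age, not information on treatment. The simulated power differences are small, and the standard error of the treatment effect is no smaller with continuous age. A standard error alone does not settle precision in logistic models, but a material loss is not shown.

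**Continuous age is not protocol wording.** The protocol calls age a factor and never says continuous. Continuous age is therefore a recommendation, not a restoration of the protocol text. It also assumes linearity on the logit scale.

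**Interactions are a further mismatch.** Section 14.1.1 contains treatment interactions that 8.1 and Table 3 omit. Fixing age alone does not make the sections agree. This is correct and should be settled in the same edit.

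**Conclusion.** The concern holds as an internal contradiction in the coding of a pre-specified covariate in both primary models, with no entry on age in section 18. Its effect on power is minor: about 0 to 2.6 points over the assumed age effects. It matters because the two codings can give opposite significance calls (about 2–7% of simulated trials) and because, with the interactions in 14.1.1, a median split is far more likely to produce separation. Separation does not always stop the software, so it can, but need not, start the fallback steps, and covariates are dropped only if exact fitting also fails.

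These figures rest on 23 per arm, an assumed age distribution and age effect, and models without center, status or baseline NEWS. The textual contradiction needs no assumption. A reader might infer that the reported model could be picked after unblinding. The wording leaves that open, but nothing in the documents shows such an intent, and SAP 4.4 places authorisation of the SAP before unblinding.

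**What to change.** Before unblinding:

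1. In SAP 8.1 replace age group with age in years, continuous, centred at the FAS mean. Use the same term in Table 3, 14.1.1 and 14.1.2.
2. Keep the median split for the subgroup tests in 8.5 only.
3. State in 8.1 and Table 3 whether the treatment interactions of 14.1.1 are in the model. If they stay, centring (or evaluating the treatment contrast at the mean age) is required, because otherwise the treatment test refers to age 0.
4. If grouped age is really intended, define its cut-point and reference population in the model section and declare it in section 18.

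The cost is a few words in the SAP, with no new data. The one statistical price is the assumption that age acts linearly on the logit scale.
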